APPENDIX 3: CAUSALITY ASSESSMENT29

ABBREVIATIONS

Abbreviation	Definition
AMI	Acute Myocardial Infarction
AT	As Treated
ATE	Arterial Thromboembolism
BMI	Body Mass Index
COC	Combined Oral Contraceptive
COC+	COC plus metformin
CRC	Colorectal Cancer
CVA	Cerebrovascular Accident
DNG	Dienogest
DRSP	Drospirenone
DVT	Deep Venous Thrombosis
EE	Ethinylestradiol
EURAS	EURopean Active Surveillance (study)
FFQ	Food Frequency Questionnaire
FU	Follow-Up
HR	Hazard Ratio
INAS	INternational Active Surveillance (study)
ITT	Intention To Treat
LNG	Levonorgestrel
OC	Oral Contraceptive
PASS	Post-Authorization Safety Study
PE	Pulmonary Embolism
SAE	Serious Adverse Event
SMAC	Safety Monitoring and Advisory Council
VTE	Venous Thromboembolism
WY	Women-years
ZEG	Berlin Center for Epidemiology & Health Research (acronym for the German term 'Zentrum für Epidemiologie & Gesundheitsforschung Berlin')

1. INTRODUCTION

In the forthcoming months new oral contraceptives (OCs) containing drospirenone (DRSP) or dienogest (DNG) as well as ethinylestradiol (EE), and metafolin (INN: levomefolate calcium) will be introduced. Oral contraceptives are an effective and popular method of birth control, with the majority of women in Europe and the US using OCs at least once in their lifetime. Over the past 50 years their safety has been improved with reductions in the estrogen and progesterone dose. Overall, the risk/benefit ratio is positive for the majority of women who need reversible and reliable contraception. However, special attention regarding oral contraceptive safety amongst women with risk factors for venous and arterial thromboembolism, as well as cancer, is necessary.

OCs containing DRSP - a progestogen that is also an aldosterone antagonist - have been available since the early 2000s. Results from the EURAS-OC [1] and the Ingenix study [2] showed that for all clinical outcomes studied - and in particular cardiovascular outcomes - there was no increased risk for users of DRSP/EE compared to users of other OCs (including OCs containing levonorgestrel (LNG)). The study results were robust enough to show non-inferiority of DRSP/EE regarding the cardiovascular outcomes of interest. In contrast, two recently published studies [3, 4] suggested that the risk of venous thromboembolism (VTE) might be slightly higher for DRSP/EE compared to LNG/EE. However, these two studies had several methodological shortcomings that resulted in an overestimation of the DRSP cohort risk [5]. Overall, the scientific discussion concerning the impact of bias and confounding on the estimates for the VTE risk associated with OC use has not been fully resolved [1-18]. The most parsimonious interpretation of the evidence that exists to date suggests that the VTE risk associated with the use of DRSP/EE and LNG/EE are similar. The addition of folate to progestogen/estrogen combinations has probably no impact on the risk of VTE. However, robust clinical data is not available and therefore an investigation of the VTE risk associated with the combination of DRSP, EE and folate is required.

In 1995, a monophasic, low-dose combined oral contraceptive (COC) containing 2 mg of dienogest and 30 µg of ethinylestradiol (DNG/EE) was introduced to the German market. For the past decade, this combined oral contraceptive has been the most widely used OC brand in Germany. A recently conducted case-control study showed that the VTE risk is similar to other low-dose COCs (including LNG/EE). The impact of folate fortification on the VTE risk of this progestogen/estrogen combination needs further elucidation.

In addition to concerns raised regarding the VTE risk profile of OCs, there has been on-going debate regarding the potential impact of OCs on the development of several cancers. Until recently, research has focused on gynecological cancers. Inconsistent

results surrounding OCs and breast cancer reveal the need for on-going surveillance [19-21]. In contrast, OCs and non-gynecological malignancies have received less attention. However, many studies suggest that progestogen/estrogen combinations - including OCs - reduce the risk of colorectal cancer (CRC) [22-24]. To date, published studies have generally had short follow-up periods and insufficient power to determine if 'duration of use' is an influential factor in the development of CRC. A recent meta-analysis on the association between oral contraceptives and CRC showed a decreased risk with 'ever use' of OCs although the analysis found no association with duration of use [25]. In contrast, Lin's analysis reported a trend towards increasing protection from CRC with increased duration of OC use (multivariate trend $p=0.09$) [26].

Folic acid supplementation has also been implicated in both the prevention and the promotion of several cancers, including colorectal cancer (CRC). However, results from different studies are conflicting. Until recently, the majority of large observational trials and randomized controlled trials assessing dietary folate and CRC seemed to suggest a moderate inverse, or no association between dietary folate and CRC [27 - 30]. However, some trials (The Netherlands Cohort Study (2002) [31], Cole (2007) [32]), and two meta-analyses by Fife et al (2009) [33] and Ebbing [34] point to a more complex picture, with a suggestion that folate supplementation may have a tumor-promoting effect in already established neoplasm. These studies have tended to examine older, predominantly male populations and extrapolating data to a young, female population is problematic. Additionally, there is some discussion as to whether the potential accelerating effect of folic acid on tumor growth is related to unmetabolized folic acid in the bloodstream. There is currently no clear evidence that folate supplementation either increases or decreases the risk of colorectal cancer. A study investigating the long-term effects of folate supplementation in a population of reproductive aged women is missing from the analysis.

Conversely, epidemiological evidence collectively suggests that low-folate diets are associated with an increased risk of malignancy, including colorectal cancer. It is possible that there is a complex interaction between folate and the cell-cycle, with folate exerting a differential effect depending on the cell status. Chronic folate deficiency seems to be associated with colorectal carcinogenesis, while high folic acid levels may have a tumor-promoting effect. On balance an oral contraceptive containing folate may be advantageous for several reasons. It may increase baseline folate levels with potential for protecting against some malignancies and concurrently decrease the risk of neural tube defects in women who become pregnant due to OC-failure, incorrect OC-use or after stopping the OC for a planned pregnancy.

Although unexpected, it is unclear whether combined oral contraceptives plus metafolin, (COC+) in general, and specifically DRSP/EE plus metafolin (DRSP/EE+) and DNG/EE plus metafolin (DNG/EE+), will alter the risk profile of established oral

contraceptives. A non-interventional post-authorization safety study (PASS) is planned to investigate the safety of this new combination of oral contraceptive with regard to cardiovascular outcomes and that of cancer and specifically colorectal cancer.

The EURAS study has demonstrated that a large, prospective, controlled, non-interventional, long-term cohort study is suitable for

1. Safety monitoring of an oral contraceptive
2. Reliable identification of relevant clinical outcomes and
3. Providing robust estimates of their incidence.

This study has a similar study design, however, the procedures for recruitment, informed consent and follow-up were modified to comply both with European and US regulations, and to ensure good recruitment rates and low loss to follow-up in a transatlantic environment. This study design has already proven to be successful in ongoing INAS studies (INAS-OC, INAS-SCORE).

The study should provide early information and regular updates on relevant clinical outcomes which will contribute to a continuous risk - benefit assessment during long-term follow up (up to 15 years).

3. STUDY DESIGN

This is a large, transatlantic, prospective, controlled, non-interventional, long-term cohort study which follows three cohorts, users of DRSP/EE+², DNG/EE+ and users of OCs containing other estrogen/progestogen combinations. The users will be grouped to 'starters' (first-ever users) 'recurrent users with a break' (re-starters and switchers with a pill intake break) and 'recurrent users without a break'. 'A break' is defined as cessation of OC intake of at least one treatment cycle. A "non-interference" approach³ will be used to provide standardized, comprehensive, reliable information on these groups of OCs under routine medical conditions. In this study, regular, active contacts with the cohort members (active surveillance) should provide all necessary information on health-related events or changes in health status during new OC use.

There will be active contacts with all study participants at baseline, every six months for the first two years, annually from years 3-5 and thereafter every 2½ years (total of

² e.g., 21-day regimen of 3mg DRSP/30µg EE and 24-day regimen of 3mg DRSP/ 20µg EE containing metafolin

³ i.e., 1) all patients who are new users of an OC - regardless of the type of estrogen or progestogen - are eligible for enrollment if they give their informed consent and 2) the recruitment of patients should not (significantly) influence the physician's prescribing behavior.

11 follow-up questionnaires)⁴. By means of these contacts, almost all relevant clinical outcomes will be captured. However, laypersons often misclassify adverse events (e.g., pain in the legs after standing a long period of time as “thrombosis” or migraine attacks as “stroke” even if modern imaging procedures do not provide any indication of the perceived event). This type of inaccuracy in patient reports requires careful validation of the reported events. This will be accomplished by contacting the relevant physicians and by reviewing relevant source documents. Under routine medical conditions, diagnosis of a VTE is not always confirmed by medical imaging. A standard algorithm will be used to classify VTE cases as “confirmed” or “not confirmed”. For cancer endpoints, a disease-specific algorithm incorporating histological diagnosis will be used (cf. section 8 and Appendix 1). At the end of the study this classification will be verified by blinded independent adjudication (cf. Appendix 2).

4. STUDY CENTERS

Recruitment of the cohort members will be conducted via a network of approximately 2,500 OC prescribing physicians (study centers) in Europe and the United States.

The combined cohort will include 80,000 women, of which about 50,000 are recruited in the United States and 30,000 in Europe. The study will be implemented in several European countries and the US. European countries selected will be geographically diverse encompassing Mediterranean, Scandinavian, Central and Eastern European countries. The sequence for starting the study in individual countries will depend upon the sequence of COC+ launches. Study participants should undergo follow-up for 12 to 15 years.

Study measures should not interfere with the prescribing behavior of physicians or with the individual needs of the participating women. Influence on the preference for specific OCs is to be avoided but significant efforts are to be undertaken to ensure standardized, comprehensive and reliable documentation of all baseline characteristics and adverse events during the follow-up period.

5. STUDY PARTICIPANTS

The study participants are women who

- are new users of an OC (first ever use, recurrent use with and without pill break)
- are willing to participate in this long-term follow-up study

⁴ planned follow-up for an individual patient at least 12 years, but can be longer based on time point of study entry. (cf. section 7)

Women will be categorized into three different groups depending on OC-user characteristics. These groups have been previously found to be important in assessing cardiovascular risk [31]. The groups are defined as 1) OC starters (first-time users), 2) recurrent users with a break (re-starters and switchers with a break) and 3) recurrent users without a pill-intake break.

There are no specific medical inclusion or exclusion criteria. However, women

- who are not cooperative/available for follow-up may be excluded from study participation
- with a language barrier will not be eligible for study inclusion

At the participating centers, all women seeking a prescription for a new OC are to be asked by their physician if they are willing to participate. The physician is to explain the nature of the study, its purpose and associated procedures, and the expected duration of follow-up for each woman prior to her study entry. Each woman is to have ample opportunity to ask questions and must be informed about her right to withdraw from the study at any time without disadvantage and without having to provide reasons for her decision. This information will be provided on an informed consent and data privacy form which must be signed by all study participants. These documents are to be approved by the relevant local Ethics Committees and the relevant Data Privacy Office, if applicable.

Once enrolled, a subject may discontinue use of OCs at any time. However, subjects will continue to be followed whether or not they remain on OCs, provided that they do not withdraw their consent. During the follow-up phase, subjects will be asked whether they have discontinued OC use or whether they have switched to another OC preparation. Information on the date and reason for discontinuation or switching during the follow-up phase will also be collected.

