11. DATA ANALYSES

The primary variable for inferential statistics is VTE. Based on available data and pharmacological/pharmacokinetic considerations the *a priori* assumption is that use of DRSP/EE+ is not associated with an increased risk of VTE compared to established OCs. That is, a statistical comparison of DRSP/EE+ and established OCs is not expected to show a difference. Therefore, a non-inferiority design to investigate the VTE risk of DRSP/EE+ was chosen. The primary analysis will be based on the comparison of the upper confidence limit for the point estimate of the VTE hazard ratio with the predefined non-inferiority limit (cf. section 12).

The null hypothesis to be tested is: $HR_{VTE} \geq 2$ (i.e., the VTE hazard ratio for DRSP/EE+ vs. established OCs is higher or equal to 2). The alternative hypothesis is: $HR_{VTE} < 2$.

Sub-analyses will include COC+, DNG/EE+, specific regimens of DRSP/EE+ (e.g., the 24-day regimen of 3mg DRSP/20µg EE) as well as starters and recurrent user with and without pill-intake break.

Safety monitoring during study conduct will be based primarily on the ITT analysis of crude data. The final analyses will include both an “as treated” (AT) and an intention-to-treat (ITT) analysis using Cox regression models. The safety conclusions of the study, however, will be based on the AT analyses because the ITT approach potentially dilutes differences between treatments.

Crude as well as adjusted hazard ratios will be calculated. The appropriate confounding variables will be built into the statistical model. Based on the expectation of a small absolute number of serious outcomes of interest the number of confounding variables will be limited to well established risk factors for these outcomes. For VTE/ATE these will include age, BMI, duration of current use, and VTE history. For Colorectal cancer age, BMI, alcohol intake and family history of CRC are planned. The final decision on the confounding variables will be made by the Safety Monitoring and Advisory Council before the first interim analysis of follow-

up data. In addition, alternative analysis will be performed with other potential baseline risks to check the appropriateness of this decision. Similar analyses will be performed for arterial thromboembolism (e.g., acute myocardial infarction and stroke), colorectal cancer and other serious adverse events.

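### Women moved without a break from DRSP/EE to DRSP/EE+ enter the test cohort as new users, and the stated primary VTE model does not settle how their continuing exposure is handled

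*Protocol*

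**What the plan says.** Protocol section 5 admits women who "are new users of an OC (first ever use, recurrent use with and without pill break"), and at the centres "all women seeking a prescription for a new OC are to be asked by their physician if they are willing to participate". Section 3 defines a break as at least one treatment cycle without intake. Nothing in sections 3, 5 or 6 excludes or marks a change to the folate version of the pill a woman already takes.

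Section 5 sorts participants into "1) OC starters (first-time users), 2) recurrent users with a break (re-starters and switchers with a break) and 3) recurrent users without a pill-intake break". Of this grouping it says: "These groups have been previously found to be important in assessing cardiovascular risk".

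The test products are marketed hormone combinations with folate added. Section 1 says that DRSP-containing OCs "have been available since the early 2000s", and that a DNG/EE pill has been sold in Germany since 1995.

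Section 11 bases the primary analysis on the VTE hazard ratio of DRSP/EE+ against established OCs, tested against a limit of 2. On adjustment: "For VTE/ATE these will include age, BMI, duration of current use, and VTE history". User status is not in that list; starters and recurrent users with and without a break appear as sub-analyses. The list is provisional: "The final decision on the confounding variables will be made by the Safety Monitoring and Advisory Council". Section 6 collects the history of OC use at baseline.

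**The concern.** A woman who goes from DRSP/EE to DRSP/EE+ without missing a cycle has not started a new hormonal exposure. She has already used the same progestogen and estrogen without an event that stopped her. If such women make up more of the DRSP/EE+ cohort than comparable women make up of the reference cohort, the DRSP/EE+ VTE rate is lowered for a reason unrelated to the product. In a non-inferiority test with an upper limit of 2, that error favours the conclusion of safety.

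Two features make over-representation plausible. The folate products are new versions of pills already on the market, so a ready pool of like-for-like switchers exists at launch. Women who simply continue an unchanged established OC are not recruited, so the reference cohort lacks the matching source. It can gain same-hormone continuers only through brand changes.

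The stated tools leave the question open. Duration of current use has two readings for this woman: from study entry, or from the start of uninterrupted use. The class of recurrent users without a break pools women who kept their hormones with women who changed them.

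**Working it through.** **1. The protocol's own figure.** Table 3 (section 12) gives the women-years (WY) needed for VTE. With rate p = margin = 9/10,000 WY in both cohorts, one-sided alpha 0.025, power 90% and k = test/reference WY:

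reference WY = (1.960 + 1.282)² × p(1−p)(1 + 1/k) / p²

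| Share | k | Computed test + reference | Table 3 |
|---|---|---|---|
| 7% | 12,543/166,635 | 12,542 + 166,627 | 12,543 + 166,635 |
| 12% | 13,256/97,204 | 13,255 + 97,198 | 13,256 + 97,204 |

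The table reproduces. User mix does not enter it, so it neither supports nor refutes the point.

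**2. Bias formula.** Let sT and sR be the shares of no-break users in the test and reference cohorts, and rT and rR their VTE rates relative to the other women in the same cohort. Without adjustment, the observed hazard ratio is the true one multiplied by

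f = [(1 − sT) + sT·rT] / [(1 − sR) + sR·rR]

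The protocol gives none of these four values; all are assumptions here.

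**3. Chance of wrongly declaring non-inferiority at a true hazard ratio of 2.** Inputs from section 12: 185,000 WY of exposure at 5 years, a reference rate of 9/10,000 WY, and a DRSP/EE+ share of 7% or 12%. Normal approximation for the log hazard ratio, SE = √(1/eT + 1/eR), where eT and eR are the expected events in the test and reference cohorts.

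Worked case with sT = 50%, sR = 30%, rT = rR = 0.5 and a 7% share:
- f = (0.50 + 0.25)/(0.70 + 0.15) = 0.75/0.85 = 0.882; observed hazard ratio 2 × 0.882 = 1.76
- eT = 12,950 × 0.0009 × 1.765 = 20.6; eR = 172,050 × 0.0009 = 154.8; SE = 0.235
- error = Φ[(ln 2 − ln 1.765)/0.235 − 1.960] = Φ(−1.43) = 0.077, against a nominal 0.025

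| sT / sR | rT / rR | f | Observed HR | Error, 7% share | Error, 12% share |
|---|---|---|---|---|---|
| 30% / 30% | equal | 1.00 | 2.00 | 0.025 | 0.025 |
| 50% / 30% | 0.8 / 0.8 | 0.96 | 1.91 | 0.04 | 0.04 |
| 50% / 30% | 0.4 / 0.4 | 0.85 | 1.71 | 0.10 | 0.13 |
| 70% / 30% | 0.8 / 0.8 | 0.91 | 1.83 | 0.06 | 0.07 |
| 70% / 30% | 0.4 / 0.4 | 0.71 | 1.41 | 0.27 | 0.39 |
| 30% / 50% | 0.8 / 0.8 | 1.04 | 2.09 | 0.015 | 0.014 |
| 30% / 50% | 0.4 / 0.4 | 1.17 | 2.34 | 0.003 | 0.002 |
| 30% / 30% | 0.5 / 0.8 | 0.90 | 1.81 | 0.06 | 0.08 |

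The last row is the case in which no-break users are equally common but mostly kept their hormones in the test cohort and mostly changed them in the reference. Equal shares then do not protect the estimate, and adjustment for the three user groups as defined would not fully remove the difference.

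**The case against.** The opposing case is substantial.

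- **Zero clock.** A reader might infer that the duration covariate restarts at zero on a switch. The protocol does not say so; it leaves the origin undefined. If duration carries over, much of the bias may be adjusted away. Defining a time origin is ordinary work for the statistical analysis plan, and on its own would be no point. What remains is that the protocol already fixes the user groups, and those groups cannot separate same-hormone continuers from women who changed hormones.
- **Certain bias.** A reader might infer that the primary result must lean towards non-inferiority. The same eligibility rule admits no-break users to the reference cohort, the protocol gives no switching patterns, and the table above shows the sign can reverse. A calculation that puts no such women in the reference cohort gives a one-sided worst case and not a fair range.
- **Existing safeguards.** Section 11 plans sub-analyses by user status, further analyses with other baseline risks, and a final covariate decision by the Safety Monitoring and Advisory Council. By definition, starters and recurrent users with a break include no one making this switch at entry, so those sub-analyses are free of the problem. This stands. However, they are sub-analyses, and the conclusion rests on the pooled hazard ratio.
- **Exclusion from the primary estimate.** This would conflict with the section 2 objective of a population representative of actual users. It would also cost exposure that is scarce: 7% of 185,000 is 12,950 WY, against 12,543 required. This stands, and exclusion belongs in a sensitivity analysis.

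**Conclusion.** The concern holds as an open route to prevalent-user bias in the pooled primary VTE hazard ratio, not as a demonstrated bias. The documents establish three things: same-hormone switchers without a break are eligible as new users, the stated duration covariate does not say how it treats them, and user status is outside the named VTE covariates although the protocol calls it important.

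Bias towards non-inferiority is the plausible direction, because the test products are folate versions of marketed pills and unchanged established use is not recruited. Under the assumption of 20 to 40 percentage points more no-break users in DRSP/EE+, with a relative VTE rate of 0.4 to 0.8 in such users, a true hazard ratio of 2 would appear as about 1.41 to 1.91. Equal mixes with equal relative rates give no bias; 20 points more in the reference gives 2.09 to 2.34. These figures assume no adjustment for user status or prior use. The change is worth making because it is cheap and protects the primary conclusion.

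**What to change.** Amend sections 3, 5 and 11, using the OC history collected at baseline:

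1. Count duration of current use from the start of uninterrupted use of the same progestogen/EE combination, regardless of folate.
2. Flag, in all cohorts, women who change preparation without a break but keep the same progestogen/EE combination. This includes same-hormone brand changes in the reference cohort.
3. Stratify the primary VTE Cox model by user status, with these continuers as a separate level. Report the hazard ratio excluding them as a sensitivity analysis and not as the primary estimate.

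**Cost.** Some extra data derivation, and a check that the baseline questionnaire records the previous preparation and the dates of uninterrupted use; section 6 does not state that level of detail. The estimate becomes slightly less precise. The continuer stratum informs the hazard ratio only as far as the reference cohort also has women and events in it, so if these are few, that part of the DRSP/EE+ exposure adds little. At a 7% share the reserve over Table 3 is only 12,950 − 12,543 = 407 WY, so the loss should be looked at when power is re-calculated on two years of follow-up, as section 12 already plans.
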